## 8.7 Validation of Statistical Analyses

Programs will be developed and maintained and output will be verified in accordance with current risk-based quality control procedures.

Tables, figures, and listings will be produced with validated standard macro programs where standard macros can produce the specified outputs.

The production environment for statistical analyses consists of Amgen-supported versions of statistical analysis software; for example, the SAS System version 9.4 or later.

## 9. Statistical Methods of Analysis

### 9.1 General Considerations

All analyses will be conducted separately for subjects enrolled from traditional sites and subjects from DCTS. Formal statistical hypothesis testing for the primary and secondary endpoints will be performed for subjects enrolled from traditional sites only. Subject characteristics for both traditional sites and DCTS will be summarized descriptively.

Summary statistics by each treatment group will be tabulated at each assessment time point if applicable. For continuous endpoints, the descriptive statistics include: number of observations, means, medians, standard deviations, standard errors, first and third quartiles, minimums and maximums, and 2-sided 95% CIs of the means (CIs will be provided for efficacy endpoints only). For categorical endpoints, the summaries will contain the number and percentage of subjects in each category.

The primary analysis method utilizing a repeated measures linear mixed effects model will include all observed data regardless of treatment adherence.

A sequential testing procedure will be used to maintain the family-wise type 1 error  $\alpha = 0.05$  between the primary and secondary endpoints following the order of modified MIDAS total score, MMD, WPAI, MFIQ physical function, MFIQ usual activity, and MFIQ social function endpoints. An endpoint will only be tested if the endpoint tested in the previous step is statistically significant at 2-sided significance level of 0.05.

## 9.2 Subject Accountability

The disposition of all randomized (enrolled) subjects will be tabulated by randomized treatment group. The summary will include the number of subjects who are randomized, the number and percent of subjects who receive/never receive IP, who complete IP, discontinue IP and reasons for discontinuing, who complete the study, and who withdraw prematurely from the study and their reasons for withdrawal.

A footnote on the subject disposition tables will include the number of subjects screened.

A summary of the study reporting period including a description of key dates will also be provided, including dates of the first and last subject enrolled and the last subject's end of study date.

## 9.3 Important Protocol Deviations

Important Protocol Deviations (IPDs) categories are defined by the study team before the first subject's initial visit and updated during the IPD reviews throughout the study prior to database lock. These definitions of IPD categories, subcategory codes, and descriptions will be used during the study. Eligibility deviations are defined in the protocol. In addition, protocol deviations related to COVID-19 control measures will be summarized and listed.

## 9.4 Demographic and Baseline Characteristics

Subject demographic and baseline characteristics will be summarized using descriptive statistics by randomized treatment group and overall study population using FAS. If multiple races have been reported for a subject, the subject will be categorized as multiple races.

At baseline, the following demographic and baseline characteristics will be summarized:

- Age
- Sex
- Ethnicity
- Race
- Height (cm)
- Weight (kg)
- Body Mass Index (BMI, kg/m^2)
- Targeted neurological disease diagnosis at baseline

- Disease duration of migraine with or without aura (years)
- Age at onset of migraine
- Number of prior migraine preventive treatment failure categories
- Summary of prior migraine preventive medication and reasons for discontinuation
- Summary of current migraine preventive treatment at baseline
- Acute headache medication used during baseline period:
  - a) Migraine-specific
  - b) Non-migraine-specific
- Monthly migraine days during baseline period
- Monthly headache days during baseline period
- Monthly acute migraine-specific medication days during baseline period
- Monthly acute migraine-specific medication days during baseline period among baseline users
- Monthly acute headache medication days during baseline period
- Monthly acute headache medication days during baseline period among baseline users
- Modified MIDAS total score, absenteeism score, and presenteeism score
- Monthly percent work impairment as measured by WPAI during baseline period
- MFIQ domain scores of function (physical, usual activities, social, and emotional) and overall impact on usual activities global item score

## 9.5 Efficacy Analyses

The primary analysis of efficacy endpoints will utilize the EAS. Subjects will be analyzed according to their randomized treatment group regardless of the actual treatment received during the study.

For primary analysis, the continuous change from baseline efficacy endpoints calculated by the method as specified in Section 5.6 will be analyzed using generalized linear mixed effect models including treatment group, scheduled visit, the interaction between treatment group and scheduled visit and the baseline value on observed data.

Detailed primary analysis methods, sensitivity analyses, and covariates included in the models are summarized in the table below.

**Table 9-1. Primary Efficacy Endpoint Summary Table**

Endpoint	Primary Summary and Analysis Method	Sensitivity Analysis
Sum of monthly changes from baseline in modified MIDAS total score over the 6-month double-blind treatment period (DBTP)  (Note: Results from individual time point during the DBTP will also be generated in the same generalized linear mixed effect model.)	

1. Summary statistics by visit using observed data at each visit and the calculated sum of each monthly change from baseline value over 6 months

2. Least squares means from a generalized linear mixed effect model including treatment group, scheduled visit, interaction of treatment and scheduled visit and baseline value using observed data

3. Test treatment difference (AMG 334 – Placebo) using a contrast from the model in #2.

	MI with assumption of MNAR (control-based pattern imputation)

**Table 9-2. Secondary Efficacy Endpoint Summary Table**

Endpoint	Primary Summary and Analysis Method	Sensitivity Analysis

Change from baseline in mean MMD over months 4, 5, and 6;                      Change from baseline in mean monthly percent work impairment as measured by WPAI over months 4, 5, and 6;
 
Change from baseline in MFIQ domain scores of function (physical function, usual activities, and social function) over months 4, 5, and 6
 
(Note: Results from individual time point during the DBTP as exploratory endpoints will also be generated in the same generalized linear mixed effect model.)
	
 
1. Summary statistics by visit using observed data at each visit, and the calculated mean monthly migraine days or mean domain scores over months 4, 5, and 6
 
2. Least squares means from a generalized linear mixed effect model including treatment group, scheduled visit, interaction of treatment and scheduled visit and baseline value using observed data
 
3. Test treatment difference (AMG 334 – Placebo) using a contrast from the model in #2.
 
	
MI with assumption of MNAR (control-based pattern imputation)

**Table 9-3. Exploratory Efficacy Endpoint Summary Table**

Endpoint	Primary Summary and Analysis Method	Sensitivity Analysis

Change from baseline in mean emotional function domain score over months 4, 5, and 6 of the 6-month DBTP, as measured by MFIQ a
 
(Note: Results from individual time point during the DBTP will also be generated in the same generalized linear mixed effect model.)
	
 
1. Summary statistics by visit using observed data at each visit, and the calculated mean domain score over months 4, 5, and 6
 
2. Least squares means from a generalized linear mixed effect model including treatment group, scheduled visit, interaction of treatment group and scheduled visit and baseline value using observed data
 
3. Test treatment difference (AMG 334 – Placebo) using a contrast from the model in #2.
 
	

Endpoints defined as change from baseline at months 1, 3, and 6 b
	
 
1. Summary statistics by visit using observed data
 
2. Least squares means from a generalized linear mixed effect model including treatment group, scheduled visit, interaction of treatment group and scheduled visit and baseline value using observed data
 
3. Test treatment difference (AMG 334 – Placebo) from the model in #2.
 
	

Footnotes defined on last page of the table

**Table 9-3. Exploratory Efficacy Endpoint Summary Table**

Endpoint	Primary Summary and Analysis Method	Sensitivity Analysis
Endpoints defined as change from baseline at each monthly assessment time point c	
 
1. Summary statistics by visit using observed data
 
2. Least squares means from a generalized linear mixed effect model including treatment group, scheduled visit, interaction of treatment group and scheduled visit and baseline value using observed data
 
3. Test treatment difference (AMG 334 – Placebo) from the model in #2.
 
	
Occurrence of at least 1 migraine-related hospitalization or outpatient HRU during the 6-month DBTP d	
 
1. Summary statistics using observed data at month 6
 
	

Page 2 of 2

a The same analysis methods will be applied to the endpoints:

Change from baseline in mean overall impact on usual activities global item score over months 4, 5, and 6 of the 6-month DBTP, as measured by MFIQ.

b The same analysis methods will be applied to the following endpoints at months 1, 3, and 6:

PHQ-9 total score,  
 GAD-7 total score,  
 PSQI total score,  
 ESS total score,  
 Patient satisfaction at work,  
 Mean reaction time, number of lapses, and number of errors as measured by PVT.

c The same analysis methods will be applied to the following endpoints at all 6 months:

Change from baseline in monthly average daily proportion of time spent in each physical activity category: sedentary, light, lifestyle, moderate, vigorous, and very vigorous,  
 Change from baseline in monthly average sleep efficiency.

d The same analysis method will be applied to all HRU endpoints.

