**Page 22 of 101**

---

Health Questionnaire; PSQI = Pittsburgh Sleep Quality Index; PVT = Psychomotor Vigilance Test; Wk = week; WPAI = Work Productivity and Activity Impairment Questionnaire

a The initial screening period is up to 3 weeks (21 days) before the baseline period begins.

b Each study visit during the double-blind treatment period (DBTP) has a window of  $\pm 3$  consecutive calendar days. The baseline period has a window of + 7 consecutive calendar days; the day 1 visit must occur 28 to 35 days after the week -4 visit date. All study visit target dates are to be calculated from the day 1 visit date. All study procedures for a given study visit are to be completed on the same day.

c A subject who discontinues the study during the DBTP (before week 24) will complete the assessments of the week 24/EOS visit.

d Format of these questionnaires will be electronic for the DCTS (within DCTS hand-held device).

e For subjects who provided informed consent for the pharmacogenetic studies, DNA will be obtained from the cell pellet collected in the plasma tube used for the biomarker development sample. Therefore, additional sampling is not required.

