#### **9.1.3 End-of-study**

The end-of-study visit occurs at week 24 or 4 weeks after last dose of IP for subjects who discontinue study. All assessments will be performed at the end-of-study visit as per Schedule of Activities ([Table 2-1](#)).

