
 
• To describe the effect of erenumab on migraine-related health resource utilization (HRU) in employed subjects with EM who have previously failed 1 or more migraine preventive treatments
 
	
 
• Occurrence of at least 1 migraine-related hospitalization or outpatient HRU during the 6-month DBTP
 
• Occurrence of at least 1 migraine-related hospitalization during the 6-month DBTP
 
• Occurrence of at least 1 migraine-related outpatient HRU during the 6-month DBTP
 
• Occurrence of at least 1 migraine-related outpatient emergency room visit during the 6-month DBTP
 
• Occurrence of at least 1 migraine-related outpatient urgent care visit during the 6-month DBTP
 
• Occurrence of at least 1 migraine-related outpatient clinic visit during the 6-month DBTP
 

 
• To evaluate the effect of erenumab compared to placebo on attention in employed subjects with EM who have previously failed 1 or more migraine preventive treatments
 
	
 
• Change from baseline in mean reaction time at months 1, 3, and 6 of the 6-month DBTP, as measured by the Psychomotor Vigilance Test (PVT)
 
• Change from baseline in number of lapses and errors at months 1, 3, and 6 of the 6-month DBTP, as measured by PVT
 

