### **Health Resource Utilization (HRU) Questionnaire**

The questionnaire is designed to collect data on HRU. Specifically, the aim is to capture frequency of migraine-related hospitalizations and outpatient visits including emergency department visits, urgent care visits, and other clinical visits. The recall period for the HRU questionnaire is 24 weeks, and the HRU questionnaire will be administered on day 1, and week 24 of the DBTP. The questionnaire assessed at the early termination visit before week 24 should only include HRU recalled since the previous assessment at day 1 to avoid collecting duplicate information. HRU will be collected at baseline and at month 6 post-baseline.

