### 5.4.2 Analysis Visits for Endpoints Based on Monthly Collection

Since the actual visit for a subject may not exactly coincide with their targeted visit date, the actual visit date is mapped to the analysis visit as in [Table 5-3](#), [Table 5-4](#), and [Table 5-5](#). Any data occurred after EOS date will not be included in the analysis.

For by-visit summaries, if more than one visit with non-missing measurement (including the unscheduled visits, ie, CPEVENT = 'UNSCHED') fall within the same visit window, the following rules will be applied according to the order described below for selecting one visit per visit window for summary:

1. Scheduled visit will be used regardless of the distance from the target day. Unscheduled visit will only be used when there is no measurement from scheduled visit in the visit window.
2. The visit closest to the target day among visits of the same type (all scheduled visits or all unscheduled visits) will be considered for analysis.
3. If two assessment dates are equidistant from the target date, the latter visit will be considered for analysis.

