## **6.2 Efficacy Analysis Set**

The respective efficacy analysis set (EAS) consists of a subset of subjects from traditional study sites or DCTS who receive at least 1 dose of IP and have a baseline value and at least 1 post baseline value for the endpoint of interest. Subjects will be analyzed according to their randomized treatment, regardless of the treatment received. Primary analysis of the efficacy endpoints will utilize the respective EAS.

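### Early-termination HRU forms dated before study day 156 have no analysis visit, so events recorded on them are left out of the six descriptive six-month HRU summaries

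*SAP*

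**What the plan says.** **Endpoint.** SAP 2.1 lists six HRU endpoints, each an occurrence over the whole treatment period. The first is "Occurrence of at least 1 migraine-related hospitalization or outpatient HRU during the 6-month DBTP".

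**Collection.** The protocol's Schedule of Activities (Table 2-1) places HRU at day 1 and at week 24/EOS. Its footnote c says: "A subject who discontinues the study during the DBTP (before week 24) will complete the assessments of the week 24/EOS visit". The SAP's HRU description (5.1.4), like protocol 9.2.2.1.9, sets the recall for an early form: "The questionnaire assessed at the early termination visit before week 24 should only include HRU recalled since the previous assessment at day 1". Protocol 9.1.3 sets the timing: "The end-of-study visit occurs at week 24 or 4 weeks after last dose of IP for subjects who discontinue study".

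**Mapping.** Under SAP 5.4.2, "the actual visit date is mapped to the analysis visit". For HRU, Table 5-5 has two rows only: baseline (last measurement on or before day 1), and week 24 with target day 169 and window 156 to 183.

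**Analysis.** The HRU row of Table 9-3 reads "Summary statistics using observed data at month 6", and its footnote d applies that method to every HRU endpoint. No model or test is planned, and SAP 9.5.2 rules out sensitivity analyses for exploratory endpoints.

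**Analysis set.** SAP 9.5 says "The primary analysis of efficacy endpoints will utilize the EAS". SAP 6.2 limits that set to dosed subjects who "have a baseline value and at least 1 post baseline value for the endpoint of interest". SAP 9.1 promises counts and percentages for categorical endpoints but does not name the base of the percentage.

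**The concern.** HRU is cumulative. A form completed at, say, day 85 that records an emergency visit since day 1 settles the endpoint for that subject: at least one event occurred in the treatment period. Nothing that happens later can reverse it. This is therefore not ordinary missing data. The plan asks sites to collect the form under a special recall instruction, then assigns forms by a date rule that leaves this one without a visit, and summarises only the visit it cannot reach.

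The stake is the accuracy of six descriptive percentages. If early leavers use care at a different rate from subjects who reach week 24, the month-6 summaries describe only the latter, while the endpoint wording covers the whole treatment period. No hypothesis test or primary or secondary result is involved.

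**Working it through.** The plan states no figure for HRU, so there is none to reproduce. The check is study-day arithmetic, a search for a rule that recovers the forms, and an illustration of size.

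**1. Unmapped days.** Post-baseline HRU window: 183 - 156 + 1 = 28 days. Days after day 1 and before the window: 155 - 2 + 1 = 154 days. A form dated on any of those 154 days has no analysis visit.

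**2. Who is typically affected.** Dose day = 1 + 7 x week. Nominal early end-of-study day = last dose day + 28 (protocol 9.1.3).

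| Last dose | Dose day | Nominal EOS day | In 156-183? |
|---|---|---|---|
| Day 1 | 1 | 29 | No (127 days early) |
| Week 4 | 29 | 57 | No (99) |
| Week 8 | 57 | 85 | No (71) |
| Week 12 | 85 | 113 | No (43) |
| Week 16 | 113 | 141 | No (15) |
| Week 20 | 141 | 169 | Yes |

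Allowing the ±3-day visit window on both dose and visit, the week 16 case reaches at most day 141 + 6 = 147, still outside. The week 20 case falls no earlier than 169 - 6 = 163, still inside. The criterion is the date of the form, not the last dose. A week 20 leaver seen before day 156 is unmapped. A subject who stops treatment but stays on study, as protocol 9.1.2 encourages, is mapped if the form is dated in the window.

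**3. Does another rule recover the form?**
- SAP 8.3 (missing data) has proration and imputation rules for monthly efficacy values and none for HRU.
- SAP 9.5.2 excludes sensitivity analyses for exploratory endpoints.
- SAP 5.6 defines subject incidence as subjects with at least one occurrence in a period over subjects entering it. Section 9.6.2 invokes this for adverse events. The HRU row of Table 9-3 does not invoke it and instead restricts the data to month 6.

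**4. Number of forms.** The documents give no dropout rate. Let d be the share leaving before day 156 and c the share of those with a form; withdrawal of consent, death and loss to follow-up (protocol 8.2.2) can leave none. Forms = 240 x d x c at traditional sites. With d assumed 5% to 15% and c anywhere from 0 to 100%:
- lowest: 240 x 0.05 x 0 = 0
- highest: 240 x 0.15 x 1 = 36
- at c = 50%: 240 x 0.05 x 0.5 = 6 to 240 x 0.15 x 0.5 = 18

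**5. Effect on a percentage (all inputs assumed).** Suppose 10% of subjects with an in-window form have an event over 168 days, 10% of all forms are early and each covers 84 days, event rates are constant, and leavers' rate is k times that of in-window subjects. The leaver proportion is 1 - 0.9^(k x 84/168) = 1 - 0.9^(k/2), and the all-forms percentage is 0.9 x 10% + 0.1 x that proportion.

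| k | Leavers with event | All forms | In-window forms only | Difference (points) |
|---|---|---|---|---|
| 1 | 5.1% | 9.5% | 10.0% | -0.5 |
| 2 | 10.0% | 10.0% | 10.0% | 0.0 |
| 3 | 14.6% | 10.5% | 10.0% | +0.5 |

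The k = 1 row matters for the remedy: with identical event rates, pooling still lowers the percentage, purely because follow-up is shorter.

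**The case against.** **A month-6 observed-data summary is a defensible complete-case choice.** A 12-week form without events cannot show six months without events, and date windows are how the SAP treats its other visit-based measures. This stands as a reason to keep the window summary. It does not justify ignoring positive early forms, which do settle the endpoint. The parallel is also incomplete. The modified MIDAS and MFIQ windows (Table 5-3) run without a gap from day 16 to 183, so an early form from day 16 onward finds a visit. PHQ-9 and the similar measures in Table 5-4 have gaps, but they are assessed at months 1, 3 and 6 and are not cumulative since day 1.

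**The early visit is labelled week 24/EOS, so it could be taken as month 6.** SAP 5.4.2 maps by actual date and Table 5-5 sets study-day limits. If the label is meant to govern, the SAP does not say so.

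**The events do not vanish.** This is correct in part. HRU data remain on the case report form, and hospitalisations that qualify as adverse events are reported as serious and tabulated. The omission is confined to the HRU summaries.

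**Stronger readings a reader might infer.** One is that the denominator is a second error: that early leavers sit in the efficacy analysis set as event-free, so the illustration would report 0.9 x 10% = 9.0%. The documents do not support that as the plan's meaning. Restricting to data observed at month 6 most naturally makes the base those subjects with an in-window form, and counting an unobserved leaver as event-free would be imputation. The 9.0% arises only if an unmapped form counts as a post-baseline value for SAP 6.2 and the whole analysis set is then used as the base; neither is stated. What remains is a secondary ambiguity: the base is not written down, and the subject-incidence definition is available but not invoked. A second inference, that the omission favours one arm or understates HRU, has no support either, since no rate by arm or by leaver status is given.

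**Conclusion.** The point holds. By the SAP's date mapping, its single post-baseline HRU window and its month-6-only summary, an early-termination HRU form dated day 2 to 155 is left out of all six HRU summaries, even when it records an event that satisfies the endpoint. This part rests on the documents alone.

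The importance is minor. The objective is descriptive, the endpoints are exploratory and untested, and no trial conclusion depends on them. Direction and size are unknown. The range of 0 to 36 forms and the shift of -0.5 to +0.5 points rest entirely on the assumed dropout, form-completion and event rates above; they show scale and are not forecasts. The unstated denominator is a clarification to make alongside, not a separate error.

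**What to change.** In SAP Table 5-5 and the HRU row of Table 9-3, before unblinding:

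1. Keep the days 156 to 183 summary and state its denominator as subjects with an HRU form in that window.
2. Add a second summary based on each subject's last HRU assessment after day 1 and up to the end-of-study date, whether at week 24 or early termination. Report subjects with at least one event over all subjects with such a form.
3. Beside that percentage, show follow-up time or an event rate per subject-month, because an event-free early leaver is not a six-month non-event.

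**Cost.** One row in each of two tables and a small amount of programming; no new data, since the forms are already on the HRU case report form. The downside is unequal follow-up in the added summary, which can lower the plain percentage (9.5% against 10.0% at equal rates in the illustration). The follow-up or rate display and the retained window summary make that visible. This is a cheap improvement, not a correction on which any trial conclusion depends.
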